Appendix 2. TFL Mocks

Appendix Table 1. Subject Disposition (All Randomized Subjects)

	B/F/TAF	SBR	All B/F/TAF
Subjects Randomized	xx	xx	xx
Subjects Randomized and Never Treated	xx	xx	xx
Subjects Randomized and Treated in the Randomized Phase	xx	xx	xx
Subjects Prematurely Discontinuing Study Drug in the Randomized Phase	xx	xx	xx
Subjects Completed the Randomized Phase but not Entered into the Extension Phase	xx	xx	xx
Subjects Entering the Extension Phase and B/F/TAF Treated	xx	xx	xx
Subjects Receiving B/F/TAF in the Randomized or Extension Phase (All B/F/TAF Analysis Set)	xx	xx	xx
Subjects Completing B/F/TAF	xx (xx%)	xx (xx%)	xx (xx%)
Subjects Prematurely Discontinuing B/F/TAF	xx (xx%)	xx (xx%)	xx (xx%)
Reasons for Prematurely Discontinuing B/F/TAF			
Adverse Event	xx (xx%)	xx (xx%)	xx (xx%)
...
Subjects Completing Study	xx (xx%)	xx (xx%)	xx (xx%)
Subjects Prematurely Discontinuing from Study	x (x.x%)	x (x.x%)	x (x.x%)
Reasons for Prematurely Discontinuing from Study			
Adverse Event	x (x.x%)	x (x.x%)	x (x.x%)
...

The denominator for percentages for each category is the number of subjects in the All B/F/TAF Analysis Set.

Appendix Table 2. Summary of Laboratory Test (unit) by Visit

All B/F/TAF Analysis Set														
	B/F/TAF (N=xxx)						SBR to B/F/TAF (N=xxx)						All B/F/TAF (N=xxx)	
	N	Mean	SD	Q1	Median	Q3	N	Mean	SD	Q1	Median	Q3	...	
Baseline	xx	xx	xx	xx	xx	xx	xx	xx	xx	xx	xx	xx	xx	...
Week x	xx	xx	xx	xx	xx	xx	xx	xx	xx	xx	xx	xx	xx	...
...
Change from Baseline at Week x	xx	xx	xx	xx	xx	xx		xx	xx	xx	xx	xx	xx	...
...

Note to programmer: the parameters include N, Mean, SD, Q1, Median and Q3 for each treatment group. If space is available, min and max will also be included. The format of the last column “All B/F/TAF” is the same as the other 2 columns.

Appendix 3. Cardiovascular or Cerebrovascular Events

An adverse event record will be flagged as a cardiovascular or cerebrovascular event if its MedDRA PT is included in the pre-specified PT list, which includes all PTs from the narrow search of the following 3 SMQs under MedDRA 21.1 provided by Gilead PVE and reviewed by Gilead medical monitors.

	SMQ Source
Cardiovascular or Cerebrovascular Events	Ischaemic central nervous system vascular conditions (SMQ) – Narrow Scope Term
	Myocardial infarction (SMQ) - Narrow Scope Term
	Other ischaemic heart disease (SMQ) - Narrow Scope Term

Appendix 4. Hepatic Events

An adverse event record will be flagged as a hepatic event if its MedDRA PT included in the pre-specified PT list, which includes all PTs from the broad search of the following 15 SMQs under MedDRA 21.1 provided by Gilead PVE and reviewed by Gilead medical monitors.

	SMQ Source
Hepatic Events (HEP)	Biliary neoplasms benign (incl cysts and polyps) (SMQ)
	Biliary malignant tumours (SMQ)
	Biliary tumours of unspecified malignancy (SMQ)
	Biliary system related investigations, signs and symptoms (SMQ)
	Biliary tract disorders (SMQ)
	Gallbladder related disorders (SMQ)
	Gallstone related disorders (SMQ)
	Cholestasis and jaundice of hepatic origin (SMQ)
	Hepatic failure, fibrosis and cirrhosis and other liver damage-related conditions (SMQ)
	Hepatitis, non-infectious (SMQ)
	Liver neoplasms, benign (incl cysts and polyps) (SMQ)
	Liver malignant tumours (SMQ)
	Liver tumours of unspecified malignancy (SMQ)
	Liver related investigations, signs and symptoms (SMQ)
	Liver-related coagulation and bleeding disturbances (SMQ)

Appendix 5. Programming Specification

- 1) For subjects who were randomized to SBR and permanently discontinued study drug in the randomized phase (subjects who were in the All Randomized Analysis Set but not in the All B/F/TAF Analysis Set), since the analysis will not include these subjects (except the disposition table and data listings), any derived variables for these subjects that will be used in the disposition table and data listings are defined as follows:
 - a) Subjects in the All Randomized Analysis Set are defined as subjects randomized into the study. IXRSRAND is the source to determine whether the subject is randomized (ie, subject with nonmissing RGMNDTN in the IXRSRAND dataset) and confirmed by the eCRF ENROLL dataset (ie, ENROLLYN = “Yes” in ENROLL dataset).
 - b) **Study Day 1 (Randomized Phase)** is defined as the day when the first dose of the randomized study drug (ie, *SBR*) was taken, as recorded on the “Randomized Phase” Study Drug Administration eCRF.
 - c) **Last Dose Date (Randomized Phase)** is defined as the latest of the randomized study drug end dates recorded on the “Randomized Phase” Study Drug Administration eCRF with “Permanently withdrawn” box checked for subjects who prematurely discontinued or completed the randomized study drug in the “Randomized Phase” according to the Study Drug Completion eCRF.
 - d) **Last Study Date** is the latest of the study drug (SBR) start dates and end dates, the clinic visit dates, and the laboratory visit dates, including the 30-day follow-up visit date, for subjects who prematurely discontinued study or who completed study according to the Study Completion eCRF. If subject died and the death date is complete (ie, not partial date) and before the imputed last study date, the complete death date should be used as the imputed last study date.
- 2) AGE calculated as follows:
 - a) AGE (years) is calculated from the number of days between the date of birth (DOB) and Day 1 (first dose date of B/F/TAF for subjects in the All B/F/TAF Analysis Set and first dose date of SBR or randomization date if never dosed for other subjects in the All Randomized Analysis Set),
 - b) Use the SAS INTCK function to determine the number of “1st-of-month days” (eg, January 1st, February 1st, March 1st) between DOB and Day 1 (inclusive),
 - c) Divide the result in (b) by 12,
 - d) AGE = the integer of the result in (c),
 - e) If the DOB and Day 1 have the month in common and the birthday is later in the month than the date of Study Day 1, then subtract one from the AGE result above.

- 3) In disposition table, the reasons for premature discontinuation are displayed in the order as they appear on the eCRF.
- 4) Body mass index (BMI) and Body Surface Area (BSA)

BMI and BSA will be calculated as follows:

- $BMI = (\text{weight [kg]} / (\text{height [meters]}^2))$
- $BSA (m^2) = \text{SQRT}([\text{Height(cm)} \times \text{Weight(kg)}] / 3600)$

All B/F/TAF baseline height and weight of the study will be used for this calculation.

- 5) Last Dose Date of B/F/TAF and Last Study Date

Last Dose Date in ADSL was defined in Section 3.8.1.

For subjects with a partial last dosing date of B/F/TAF (ie, month and year of last dose are known), the minimum of {(death date, if available), (the latest of the dispensing dates of B/F/TAF bottles, B/F/TAF start dates and end dates (based on EX dataset), and the imputed last dose date [day imputed as 15])} will be used as the final imputed last dose date. However if dispensing date's month is after last dose date's month, data query is needed.

Last Study Date is the latest of the study drug start dates and end dates, the clinic visit dates, and the laboratory visit dates, including the 30-day follow-up visit date, for subjects who prematurely discontinued study or who completed study according to the Study Completion eCRF. If study drug start dates or end dates is partially missing (ie, only year and month are known), the day will be imputed as 15 for the purpose of this analysis.

- 6) Treatment Group Presented in the Listings

In data listings, the treatment group will be presented as follows:

B/F/TAF: subjects who were randomized into B/F/TAF group in the randomized phase, either entered into the extension phase or not;

SBR: subjects who were randomized into SBR group in the randomized phase and did not enter into the extension phase of B/F/TAF;

SBR to B/F/TAF: subjects who were randomized into SBR group in the randomized phase and entered into the extension phase of B/F/TAF.

7) Toxicity Grades:

- i) For toxicity grade summaries, include all postbaseline graded results up to 30 days after the last dose of B/F/TAF, not just those used in by-visit summaries.
- ii) For glucose grading, as specified in SAP Section 7.2.2.1, the treatment-emergent flag cannot be determined for nonfasting glucose (including glucose results without a known fasting status). As a result, these records will be excluded from the “Maximum Treatment-emergent Toxicity Grade” summary in the “Treatment-emergent Laboratory Abnormalities” or “Treatment-emergent Grade 3 or 4 Laboratory Abnormalities” summary tables. In addition, fasting glucose and non-fasting glucose will be listed as two separate laboratory tests in the “Laboratory Abnormalities” and “Grade 3 or 4 Laboratory Abnormalities” listings. Only a maximum postbaseline toxicity flag will be displayed and the treatment-emergent flag will not be displayed for nonfasting glucose as the treatment-emergent flag cannot be determined for nonfasting glucose.

8) Graded Laboratory Abnormalities Summary

The following labels will be used for treatment-emergent laboratory abnormalities and treatment-emergent Grade 3 or 4 laboratory abnormalities summary tables and listings:

Battery	Lab Test Label Used in l-labtox Listing	Toxicity Direction	Lab Test Label Used in t-labtox Table
Hematology	Hemoglobin	Decrease	Hemoglobin (Decreased)
	Neutrophils	Decrease	Neutrophils (Decreased)
	Platelets	Decrease	Platelets (Decreased)
	WBC	Decrease	WBC (Decreased)
Chemistry	Albumin	Decrease	Albumin (Decreased)
	Alkaline Phosphatase	Increase	Alkaline Phosphatase (Increased)
	ALT	Increase	ALT (Increased)
	Amylase	Increase	Amylase (Increased)
	AST	Increase	AST (Increased)
	Bicarbonate	Decrease	Bicarbonate (Decreased)
	Corrected Calcium	Increase	Corrected Calcium (Hypercalcemia)
	Corrected Calcium	Decrease	Corrected Calcium (Hypocalcemia)
	Creatine Kinase (CK)	Increase	Creatine Kinase (Increased)
	Creatinine	Increase	Creatinine (Increased)
	GGT	Increase	GGT (Increased)
Lipase	Increase	Lipase (Increased)	
	Magnesium	Decrease	Magnesium (Hypomagnesemia)

Battery	Lab Test Label Used in l-labtox Listing	Toxicity Direction	Lab Test Label Used in t-labtox Table
	Phosphate	Decrease	Phosphate (Hypophosphatemia)
	Serum Glucose (Fasting)	Increase	Serum Glucose (Fasting, Hyperglycemia)
	Serum Glucose (Fasting)	Decrease	Serum Glucose (Fasting, Hypoglycemia)
	Serum Glucose (Nonfasting)	Increase	Serum Glucose (Nonfasting, Hyperglycemia)
	Serum Glucose (Nonfasting)	Decrease	Serum Glucose (Nonfasting, Hypoglycemia)
	Serum Potassium	Increase	Serum Potassium (Hyperkalemia)
	Serum Potassium	Decrease	Serum Potassium (Hypokalemia)
	Serum Sodium	Increase	Serum Sodium (Hypernatremia)
	Serum Sodium	Decrease	Serum Sodium (Hyponatremia)
	Total Bilirubin	Increase	Total Bilirubin (Hyperbilirubinemia)
	Total Cholesterol (Fasting)	Increase	Total Cholesterol (Fasting, Hypercholesterolemia)
	Triglycerides (Fasting)	Increase	Triglycerides (Fasting, Increased)
	LDL (Fasting)	Increase	LDL (Fasting, Increased)
	Urea Nitrogen (BUN)	Increase	Urea Nitrogen (Increased)
	Uric Acid	Increase	Uric Acid (Hyperuricemia)
	Uric Acid	Decrease	Uric Acid (Hypouricemia)
	Prothrombin Intl. Normalized Ratio (INR)	Increase	N/A
	Prothrombin Time (PT)	Increase	N/A
Urinalysis	Urine Blood (Dipstick)	Increase	Urine RBC (Hematuria, Quantitative or Dipstick)*
	Urine Glucose	Increase	Urine Glucose (Glycosuria)
	Urine Protein	Increase	Urine Protein (Proteinuria)
	Urine RBC	Increase	Urine RBC (Hematuria, Quantitative or Dipstick)*

* Due to the reflexive nature of the quantitative urine RBC test, results will be combined with the dipstick test of urine blood as described below. General rule is that urine RBC (Quantitative) should always be used first (if available), no matter it is collected at the same time of Urine Blood (Dipstick) or not. The combined Urine RBC (hematuria, Quantitative or Dipstick) toxicity grade will be used for “Maximum treatment-emergent toxicity grade” summary.

Is Post-BL Urine RBC (Quant.) Result Available?	Is BL Urine RBC (Quant.) Result Available?	Is Post-BL Urine Blood (Dipstick) Result Available?	Is BL Urine Blood (Dipstick) Result Available?	How to Determine Treatment-Emergent Toxicity for “Urine RBC (Hematuria, Quantitative or Dipstick)”
Yes	Yes	-	-	Compare post-BL Urine RBC (Quant.) toxicity grade to BL Urine RBC (Quant.) toxicity grade. If post-BL toxicity is greater than BL toxicity, then treatment-emergent
Yes	No	-	-	Treatment-emergent. Use post-BL Urine RBC (Quant.) toxicity grade.
No	-	Yes	Yes	Compare post-BL Urine Blood (Dipstick) toxicity grade to BL Urine Blood (Dipstick) toxicity grade. If post-BL toxicity is greater than BL toxicity, then treatment-emergent
No	-	Yes	No	Treatment-emergent. Use post-BL Urine Blood (Dipstick) toxicity grade.
No	-	No	-	Do not count subject in the denominator for “Urine RBC (Hematuria, Quantitative or Dipstick)”

BL = Baseline. Quant = Quantitative. “-” means any value can be present (or it can be missing), as it does not affect the classification

9) Renal related laboratory evaluation

a) Unit conversion for renal safety tests derived from related tests with conventional units

- i) Urine RBP (ug/L) to creatinine (mg/dL) ratio: $1 \text{ (ug/L)} / \text{(mg/dL)} = 100 \text{ x ug/g}$
- ii) Urine Beta-2-microglobulin (mg/L) to creatinine (mg/dL) ratio: $1 \text{ (mg/L)} / \text{(mg/dL)} = 10^5 \text{ ug/g}$
- iii) Urine Albumin (mg/dL) to creatinine (mg/dL) ratio: $1 \text{ (mg/dL)} / \text{(mg/dL)} = 1000 \text{ x mg/g}$

b) Calculation of ratios:

To calculate laboratory ratios (eg, urine RBP to creatinine ratio), the lab value of each test in the ratio needs to be from the same accession number; if any test value used for the ratio calculation from the same accession number is missing, then the ratio is not calculable (ie, missing).

- 10) For figures, if at a visit where n (sample size) for any treatment group ≤ 5 , data for that treatment group will not be displayed at the visit in figure (except the Kaplan-Meier figure), but all data will be included in the corresponding table summary.
- 11) Puerto Rico was combined with the United States when we evaluate the treatment effect across countries.
- 12) LDL: Conversions between 2nd and 3rd generations

LDL was analyzed by 2 different assays in the study: 2nd generation (including RCT2394, RCT2312, and RCT2811) and 3rd generation (RCT3870). Samples collected at earlier visits were analyzed using LDL 2nd generation assay. Samples collected at later visits were analyzed using LDL 3rd generation assay. The conversion formulas are as follow:

$$\text{2nd Gen (mmol/L)} = (\text{3rd Gen} - 0.0626)/0.882$$

$$\text{3rd Gen (mmol/L)} = (0.882 \times \text{2nd Gen}) + 0.0626$$

For this analysis, since most of the LDL tests were from the 2nd generation, we only requested conversion from 3rd generation to 2nd generation.

For the analysis of change from baseline in fasting direct LDL: the sample analyzed by LDL 3rd generation assay will be converted to 2nd generation as a new record with test codes of LIP.LDL.00.02 in raw data. During ADaM stage, a derived parameter code (FLDL2) for “Fasting LDL Cholesterol 2ND GEN Combined” will be generated to pool the records from both original (including test codes RCT2394, RCT2312, and RCT2811) and converted (LIP.LDL.00.02) 2nd generation results to calculate the change from baseline in fasting direct LDL.

For the analysis of toxicity grade for fasting direct LDL: toxicity grade will be based on the Gilead grading results (ie, toxgrg) from original values before conversion. In another words, during ADaM stage, a derived parameter code (FLDLTOX) for “Fasting LDL Cholesterol for Toxicity” will be generated to pool the records from 2nd generation (including RCT2394, RCT2312, and RCT2811) and 3rd generation (ie, RCT3870) to derive treatment-emergent toxicity grades, maximum postbaseline toxicity grades, etc.

SAP_Final_GS-US-380-1961_V1.0

ELECTRONIC SIGNATURES

Signed by	Meaning of Signature	Server Date (dd-MMM- yyyy hh:mm:ss)
PPD	Biostatistics eSigned	22-Dec-2018 00:00:48
PPD	Clinical Research eSigned	22-Dec-2018 00:47:59

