### 6.4. Treatment Assessments (Weeks 4-48)

The following evaluations are to be completed at the end of Weeks 4, 8, 12, 24, 36, and 48 unless otherwise specified.

Study visits are to be completed within  $\pm$  2 days of the protocol-specified visit date based on the Day 1 visit through Week 12 and completed within  $\pm$  6 days at Week 24 and Week 36, unless otherwise specified. The visit window at Week 48 will be  $\pm$  6 weeks of the protocol-specified visit date, and these clinical visit windows coincide with the Week 48 statistical analysis window for HIV-1 RNA.

Regularly scheduled evaluations will be made on all subjects whether or not they continue to receive study drug.

- Review of AEs and changes in concomitant medications
- Complete physical examination (**Weeks 24 and 48**) (urogenital/anorectal exams will be performed at the discretion of the Investigator) or symptom-directed physical examination as needed
- Vital signs measurement (blood pressure, pulse, respiration rate, and temperature), including weight
- 12-lead ECG performed supine (**Weeks 24 and 48**)
- Urine collection for the following laboratory procedures:
  - Urinalysis
  - Urine albumin, urine creatinine, urine protein, retinol binding protein and beta-2 microglobulin (**Weeks 24 and 48**)
  - Urine pregnancy test (females of childbearing potential only); positive urine pregnancy tests will be confirmed with a serum test. If the test is positive, subjects on GS-9883/F/TAF will be discontinued.
  - Urine storage sample for possible additional clinical testing

- Blood sample collection for the following laboratory analyses:
  - Chemistry profile: alkaline phosphatase, AST, ALT, GGT, total bilirubin, direct and indirect bilirubin, total protein, albumin, bicarbonate, BUN, calcium, chloride, creatinine, glucose, phosphorus, magnesium, potassium, sodium, uric acid, and amylase (reflex lipase testing is performed in subjects with total amylase  $> 1.5 \times$  ULN). At Weeks 12, 24 and 48, analyses of glucose will be done as part of the fasting metabolic assessments and not as part of the chemistry profile. At Weeks 24 and 48, TSH will also be analyzed.

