# An overlap between the Grade 1 scale and the Lab's normal range for absolute neutrophils may result for pediatric subjects. Please follow the Gilead convention of grading any result within the LLN and ULN a 0.

CHEMISTRY				
	Grade 1	Grade 2	Grade 3	Grade 4
Hyponatremia	130 to <LLN mEq/L 130 to <LLN mmol/L	125 to < 130 mEq/L 125 to < 130 mmol/L	121 to < 125 mEq/L 121 to < 125 mmol/L	< 121 mEq/L < 121 mmol/L
Hypernatremia	>ULN to 150 mEq/L >ULN to 150 mmol/L	> 150 to 154 mEq/L > 150 to 154 mmol/L	> 154 to 159 mEq/L > 154 to 159 mmol/L	> 159 mEq/L > 159 mmol/L
Hypokalemia Adult and Pediatric ≥ 1 Year	3.0 to <LLN mEq/L 3.0 to <LLN mmol/L	2.5 to < 3.0 mEq/L 2.5 to < 3.0 mmol/L	2.0 to < 2.5 mEq/L 2.0 to < 2.5 mmol/L	< 2.0 mEq/L < 2.0 mmol/L
Infant <1 Year	3.0 to 3.4 mEq/L 3.0 to 3.4 mmol/L	2.5 to < 3.0 mEq/L 2.5 to < 3.0 mmol/L	2.0 to < 2.5 mEq/L 2.0 to < 2.5 mmol/L	< 2.0 mEq/L < 2.0 mmol/L
Hyperkalemia Adult and Pediatric ≥ 1 Year	5.6 to 6.0 mEq/L 5.6 to 6.0 mmol/L	> 6.0 to 6.5 mEq/L > 6.0 to 6.5 mmol/L	> 6.5 to 7.0 mEq/L > 6.5 to 7.0 mmol/L	> 7.0 mEq/L > 7.0 mmol/L
Infant <1 Year	>ULN to 6.0 mEq/L >ULN to 6.0 mmol/L	> 6.0 to 6.5 mEq/L > 6.0 to 6.5 mmol/L	> 6.5 to 7.0 mEq/L > 6.5 to 7.0 mmol/L	> 7.0 mEq/L > 7.0 mmol/L

CHEMISTRY				
	Grade 1	Grade 2	Grade 3	Grade 4
Hypoglycemia Adult and Pediatric ≥ 1 Month	55 to 64 mg/dL 3.03 to 3.58 mmol/L	40 to < 55 mg/dL 2.20 to < 3.03 mmol/L	30 to < 40 mg/dL 1.64 to < 2.20 mmol/L	< 30 mg/dL < 1.64 mmol/L
Infant, < 1 Month	50 to 54 mg/dL 2.8 to 3.0 mmol/L	40 to < 50 mg/dL 2.2 to < 2.8 mmol/L	30 to < 40 mg/dL 1.7 to < 2.2 mmol/L	< 30 mg/dL < 1.7 mmol/L
Hyperglycemia, Nonfasting	116 to 160 mg/dL 6.42 to 8.91 mmol/L	> 160 to 250 mg/dL > 8.91 to 13.90 mmol/L	> 250 to 500 mg/dL > 13.90 to 27.79 mmol/L	> 500 mg/dL > 27.79 mmol/L
Hyperglycemia, Fasting	110 to 125 mg/dL 6.08 to 6.96 mmol/L	>125 to 250 mg/dL >6.96 to 13.90 mmol/L	>250 to 500 mg/dL >13.90 to 27.79 mmol/L	>500 mg/dL >27.79 mmol/L
Hypocalcemia (corrected for albumin if appropriate*) Adult and Pediatric ≥ 2 Years	7.8 < LLN mg/dL 1.94 to < LLN mmol/L	7.0 to < 7.8 mg/dL 1.74 to < 1.94 mmol/L	6.1 to < 7.0 mg/dL 1.51 to < 1.74 mmol/L	< 6.1 mg/dL < 1.51 mmol/L
Pediatric ≥ 7 days - 2 Years	7.8 to 8.4 mg/dL 1.94 to 2.10 mmol/L	7.0 to < 7.8 mg/dL 1.74 to < 1.94 mmol/L	6.1 to < 7.0 mg/dL 1.51 to < 1.74 mmol/L	< 6.1 mg/dL < 1.51 mmol/L

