7.2.2.1. Treatment Emergent Laboratory Abnormalities

Treatment-emergent laboratory abnormalities are defined as values that increase at least 1 toxicity grade from baseline at any postbaseline time point, up to 30 days from the last dose date of B/F/TAF. If the relevant baseline laboratory value is missing, any abnormality of at least Grade 1 observed within the time frame specified above will be considered treatment-emergent.

Fasting glucose and nonfasting glucose (including glucose results without a known fasting status) are graded based on different grading scales as specified in the protocol.

Treatment-emergent laboratory abnormalities will be summarized for fasting glucose. Maximum postbaseline grade, instead of treatment-emergent grade, for nonfasting glucose (including glucose results without a known fasting status) will be summarized, as nonfasting glucose was not assessed at baseline visit for most of the subjects; therefore, an abnormality is treatment-emergent or not cannot be determined for these subjects.

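### The SAP applies the fasting/nonfasting split to low glucose, where the protocol has a single scale, so nonfasting lows get no treatment-emergent status

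*SAP*

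**What the plan says.** SAP 7.2.2.1 states that fasting glucose and nonfasting glucose (the latter including results of unknown fasting status) "are graded based on different grading scales as specified in the protocol". Fasting results get treatment-emergent grades. For the rest, the SAP summarizes "Maximum postbaseline grade, instead of treatment-emergent grade, for nonfasting glucose", because most women had no nonfasting glucose at the baseline visit.

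Appendix 5 carries this into programming. Item 7(ii) says the treatment-emergent flag cannot be set for nonfasting or unknown-status results. It continues "As a result, these records will be excluded from the" maximum treatment-emergent grade summary of the treatment-emergent table and the Grade 3 or 4 table. Nothing limits this to high values. The next sentence, which concerns listings only, adds that "fasting glucose and non-fasting glucose will be listed as two separate laboratory tests". Item 8 then defines separate fasting and nonfasting table rows in each direction; one label begins "Serum Glucose (Nonfasting, Hypoglycemia".

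Protocol Appendix 4 (Chemistry) has two rows for high glucose, one of them headed "Hyperglycemia, Nonfasting". For low glucose in adults it has one row, with Grade 1 at "55 to 64 mg/dL 3.03 to 3.58 mmol/L" and no fasting condition in any grade.

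**The concern.** The SAP bases the split on the protocol having two scales. That is true for high glucose and untrue for low glucose. With a single scale, a nonfasting low and a fasting pre-dose value are graded on the same cut-offs, so whether the grade has risen can be determined.

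What is at stake is how hypoglycemia is reported in the final B/F/TAF safety tables. It is divided between a treatment-emergent row (fasting) and a maximum-postbaseline-grade row (nonfasting). The two rows use different definitions and may share women, so they cannot be added to give the number with treatment-emergent hypoglycemia. A woman whose only Grade 3 or 4 result is a nonfasting glucose below 40 mg/dL is also left out of the overall maximum-grade line.

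**Working it through.** The documents state no figure on this point, so there is none to reproduce. The check compares the texts and counts scheduled draws.

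**1. Scales**

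| Direction | Protocol Appendix 4 (adult) | SAP Appendix 5, item 8 |
|---|---|---|
| High | Two scales: Grade 1 is 110–125 mg/dL fasting, 116–160 mg/dL nonfasting | Two rows |
| Low | One scale: Grade 1 is 55–64, Grade 2 is 40 to <55, Grade 3 is 30 to <40, Grade 4 is <30 mg/dL | Two rows |

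A value of 112 mg/dL is Grade 1 if fasting and ungraded if not, so fasting status matters in the high direction. A value of 38 mg/dL is Grade 3 either way.

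**2. Is there a baseline for a nonfasting low?** SAP 3.8.1 takes the last nonmissing value on or before Study Day 1, for all assessments.
- Protocol 6.2.2 collects fasting glucose at Day 1.
- If that draw is delayed (a woman who has not fasted may return within 72 hours), Protocol 6.2.1 supplies a Screening chemistry-profile glucose.
- Women moving from SBR to B/F/TAF have a fasting glucose at Week 48, the visit at which B/F/TAF is first dispensed.

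All of these are gradable on the one hypoglycemia scale.

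**3. What if baseline were missing?** Protocol 8.6.3 and the opening paragraph of SAP 7.2.2.1 both count any Grade 1 or higher value as treatment-emergent in that case. The hematuria rule in Appendix 5 item 8 does the same: a quantitative result with no quantitative baseline is called treatment-emergent. For glucose, item 7(ii) takes the opposite course, while SAP 7.8 declares no change from the protocol's safety analysis.

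**4. Scheduled draws affected**
- To Week 48 (Protocol 6.4): visits at Weeks 4, 8, 12, 24, 36 and 48, so 6 draws. "At Weeks 12, 24 and 48, analyses of glucose will be done as part of the fasting metabolic assessments", so 3 are fasting. Nonfasting: 6 − 3 = 3 (Weeks 4, 8, 36).
- Extension (Protocol 6.5.1; Appendix 2, footnote j): visits every 12 weeks (60, 72, 84, 96), fasting every 24 weeks (72, 96). Nonfasting: 4 − 2 = 2.
- B/F/TAF group to Week 96: 3 + 2 = 5 of 6 + 4 = 10.
- SBR to B/F/TAF over 48 weeks of extension: 2 of 4.

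Three limits apply to this count. The SAP classifies by recorded fasting status, so a sample drawn fasted at Week 4, 8 or 36 could count as fasting and lower the share. The early-discontinuation and 30-Day Follow-Up visits also draw chemistry-profile glucose with no fasting requirement; they are not counted here and would raise it slightly. Footnote j omits Week 12 from the visits where fasting glucose replaces the chemistry-profile glucose, but Week 12 has a fasting metabolic draw either way.

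**5. Effect on the maximum-grade line.** Item 8 says the combined hematuria grade feeds the maximum treatment-emergent grade summary, which indicates that this line runs across tests. Under item 7(ii) a nonfasting low does not feed it.

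**The case against.** The strongest defense is that nothing is hidden. Item 8 gives nonfasting hypoglycemia its own table row, whereas INR and PT have none. Maximum postbaseline grade counts every postbaseline low whatever the baseline, so for those records it is at least as inclusive as a treatment-emergent count. The convention is disclosed, the protocol collects the two kinds of glucose in different panels, and SAP 7.2.2.1 gives a second reason: most women had no nonfasting value at the baseline visit. Under Protocol 7.1.3, a laboratory abnormality that requires intervention or leads to interruption of study drug is also recorded as an adverse event.

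Much of this stands. A reader might infer that nonfasting lows are missing from the report; they are not, since the row and the listings carry them. The second reason does not rescue the exclusion: on a single scale the baseline need not be nonfasting, and the SAP's missing-baseline rule would apply if there were none. Using different record sets for high and low glucose simply follows Appendix 4.

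A reader might also infer that reported hypoglycemia would be halved. With an assumed equal, independent risk p per draw, the share flagged to Week 48 is 1 − (1 − p)^3 on fasting draws against 1 − (1 − p)^6 on all draws: 0.60% against 1.19% at p = 0.2%, 1.49% against 2.96% at 0.5%, and 2.97% against 5.85% at 1%. The documents do not support this as a finding. They give no hypoglycemia rate, equal fed and fasted risk is assumed, and the comparison ignores the nonfasting row. No planned toxicity-grade summary stops at Week 48, since item 7(i) takes all results to 30 days after the last dose.

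Nor does the metformin entry in Protocol Table 5-1 add weight. It recommends monitoring and mentions dose adjustment, but says nothing about hypoglycemia.

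**Conclusion.** Wrong as written, but minor. For low glucose, the different-scales premise in SAP 7.2.2.1 contradicts Protocol Appendix 4, and item 7(ii)'s claim that treatment-emergent status cannot be determined does not hold under the SAP's own baseline and missing-baseline rules.

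The consequence is limited to presentation. Nonfasting and unknown-status lows get no treatment-emergent flag, no row counts women with treatment-emergent hypoglycemia, and these results do not enter the overall maximum-grade line. The reach of 3 of 6 draws to Week 48 and 5 of 10 to Week 96 is by schedule and assumes that chemistry-profile samples are not recorded as fasted. The number of women affected is unknown. This SAP covers only the descriptive final analysis of B/F/TAF, so no treatment comparison and no primary-endpoint result depends on it.

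**What to change.** - In SAP 7.2.2.1, limit the statement about different scales, and the switch to maximum postbaseline grade, to hyperglycemia.
- In Appendix 5 item 7(ii), limit the exclusion to hyperglycemia.
- In item 8, replace the two glucose rows in the decrease direction with one, Serum Glucose (Hypoglycemia). Use all glucose results regardless of fasting status, graded on the single Appendix 4 scale against the last pre-dose glucose (SAP 3.8.1), with the existing missing-baseline rule.
- Include that row in the treatment-emergent tables and in the maximum-grade line. The listings can still show fasting status.

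The cost is a few words in two places, one table row and the matching program change, with no new data. SAP Section 1 already provides for changes after finalization to be documented in the clinical study report. If the split is kept, SAP 7.8 should declare it as a departure and the scale statement should still be corrected.
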